7.8. Prior and Concomitant Medications and Therapies

7.8.1 Permitted

Subjects will be allowed to continue with their usual necessary medical therapies, with no medically unnecessary changes in their diet or overall lifestyle. If medical conditions exist at the start of the study that require drug therapy during the study, those conditions and any concomitant medications prescribed should be recorded in the subject's source documents and the appropriate section of the CRF.

Subjects must abstain from exclusionary procedures/medications/therapies as listed under the Exclusion Criteria for the duration of the study.

Investigational Device: ThermiRF

Protocol No.: Thermi_0005

Version Date: Final 10-May-2016

8. STUDY PROCEDURES

Study procedures as described in this section are depicted in the schedule of evaluations (Appendix 1).

8.1. VISIT 1 (Screening) - (Day 1)

Subjects who signed the informed consent at Visit 1 will have the following assessments performed:

- Inclusion and exclusion criteria
- Medical and Medication History
- Demographic and baseline characteristics
- Brief physical exam and Medical Clearance
- Vitals including height and weight
- Photography (2D and 3D)
- Confirmation of “Skin Laxity Severity” by the investigator
- Elasticity measurement

Subjects who meet all required entry criteria will be enrolled in the study, and will be a **subject ID** starting with **“0116”** and continuing in sequential order until enrollment is met (i.e., 7016). The first two digits represent the subject number and the last two digits represent the year when the study is initiated.

Enrolled subjects will be scheduled for Visit 2 promptly after Visit 1. A prescription slip for an antibiotic and an analgesic medication will be dispensed at the discretion of the investigator with instructions as follow:

INSTRUCTION

“Begin taking the antibiotics the day before the procedure at Visit 2, and continue taking as prescribed until the dose regimen is completed. The analgesic should be brought to the research site at which time, the first dose will be taken”

“Make arrangements to have a legal representative drive to and from the research site.”

8.2. VISIT 2 (Treatment)

Upon arrival, subjects will have the following assessments performed:

- Verify conformance with eligibility criteria
- Urine pregnancy test (*must be performed prior to treatment at V1 or V2*)

[figure not shown]
Provided the subject conforms to all entry criteria, the subject will be prepared for surgery and the visit will proceed as follow:

The subjects will be placed in a sitting or supine position. Using a surgical pen or marker the investigator will outline the treatment area and the area will be anesthetized using tumescent solution containing lidocaine and epinephrine. Sufficient time will be allowed for the anesthesia to take effect prior to the surgical procedure

Up to three small incisions measuring approximately 2 mm in length will be made to the right and left of the jaw line below the ear lobe, and below the chin. Each incisions will act as the point of entry for the investigational device probe.

The depth of penetration is approximately 2 mm below the dermis. The affected area of the neck will be infused with standard tumescent Hunstad formula (50-100cc). The investigator will proceed with the treatment by inserting the electrode to the distal portion of the first pass. Once in position, and the electrode temperature will be brought to the “procedure set temperature” in accordance with the suggested temperature ranges below (Figure 4).

Figure 4: Suggested Temperature Ranges

The investigator will begin to slowly withdraw the electrode to ensure the temperature achieves the level of the set temp.

[figure not shown]
Investigational Device: ThermiRF

Protocol No.: Thermi_0005

Version Date: Final 10-May-2016

The pass is repeated in a “fanning” manner to ensure treatment of the entire neck area is achieved (Figure 5).

Figure 5: Treatment Passes

The surface of the skin must reach a temperature between 45-47°C.

At the conclusion of the treatment, hypoallergenic tape may be applied and the use of a neck garment required in support of tissue repair post treatment. The duration of garment use is approximately 3-5 days or as directed by the investigator.

Subjects will be sent home and will be instructed on the following:

“Do not drive, engage in physical exercise or operate heavy machinery the day of the procedure at Visit 2 and for approximately 14 to 21 days for physical exercise including heavy lifting.”

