6. INVESTIGATIONAL PLAN

6.1. Overall Study Design and Plan

This is an open-label, single-center, single-treatment prospective evaluation of the ThermiRF device in the treatment of submental skin laxity. The purpose of this prospective study is to determine the effectiveness and safety of the ThermiRF device in achieving overall submental lift.

In this study, “Lift” is defined as a ≥ 20 mm² lift of the submental area after the ThermiRF treatment.

A total of 70 male and female healthy volunteers between the age of 35 and 65 will be considered for this study. Subjects who sign the informed consent form and meet all entry criteria will be enrolled in this study and will be assigned a unique number/code to preserve confidentiality.

A total of six study visits are planned as described below:

- Visit 1: Screening visit – (Day 1)
- Visit 2: Single Treatment visit
- Visit 3: Day 30 safety assessment (± 7 to 14 days)
- Visit 4: Day 60 safety and Image capture for validation exercise (± 7 to 14 days)
- Visit 5: Day 90 safety and effectiveness follow-up visit (± 7 to 14 days)
- Visit 6: Day 180 safety and effectiveness follow-up visit - (± 7 to 14 days)

Photo images (2D and 3D) will be collected at Visits 1, Visit 4 (on first 30 subjects only), and at Visits 5 and 6 using a standard camera (2D) and the Vectra XT system (3D). The purpose of the photos are to quantitatively and qualitative evaluate treatment effectiveness using objective and subjective assessments to measure physical changes to the skin’s microstructure and aesthetic skin features over time.

A skin elasticity assessment using the Cutomer® will be collected at Visits 1 (screening), 5 (Day 90) and 6 (Day 180) to assess if any biomechanical changes of the skin occurred as a result of the ThermiRF treatment.

Safety assessments will be collected using the Numerical Rating Scale (NRS) a 10-point scale, and adverse events reports (observed or reported).

The overall study duration is approximately 12 months (i.e., 5-6 month recruitment period and 6 month study visits).

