6.3.2 Exclusion Criteria

Subjects presenting with any of the following will not be included in the study:

- Excessive subcutaneous fat on the submental area
- Use within 24 hours preceding surgery of ibuprofen, acetaminophen, any other analgesics, anti-inflammatory products, or any products including herbals and supplements that could interfere with the clinical assessments of this study (other than drugs used for anesthesia);
- History of cosmetic treatments on the face and neck including but not limited to: facial skin tightening procedures within the *past year*, injectable fillers of any type, Botox on the lower face, ablative resurfacing laser treatment, none ablative, rejuvenative laser or light treatment within the *past six months*, deep facial peels, dermabrasion, face lift, neck lift, blepharoplasty or brow lift, contour threads or other.
- History or current injury to the Head and Neck.
- Severe solar elastosis

Investigational Device: ThermiRF

Protocol No.: Thermi_0005

Version Date: Final 10-May-2016

- Clinically significant facial wounds, lesions or acute infections including cystic acne, dermatitis, lupus or other immunodeficiency affecting the dermis
- Presence of metal stents or facial implants
- Pregnant or planning pregnancy prior to the end of study participation
- Current or past history of smoking
- History or current diagnosis of cancer of any type
- History of uncontrolled cardiovascular disease(i.e. myocardial infarction, hypertension, hypercholesterolemia, peripheral vascular disease, other)
- Known hypersensitivity to local anesthetic medications
- History, or current bleeding disorders (i.e. hemophilia or von Willebrand disease), or anticipated treatment with prescription anticoagulants
- Possesses a surgically implanted electronic device (i.e. pacemaker)
- History of AIDS/HIV
- Serious mental health illness such as dementia or schizophrenia; psychiatric hospitalization in the past two years
- Developmental disability or cognitive impairment that would preclude adequate comprehension of the informed consent form and/or ability to follow study subject requirement and/or record the necessary study measurements
- A family member of the investigator or an employee of the investigator.
- Participation in any other investigational study **within 30 days prior to consent**;

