9. ASSESSMENTS

9.1. Clinical Evaluations

The following clinical evaluations will be conducted during the study review:

- **Medical and medication history** – An assessment of the participant’s health status prior to enrollment to ascertain appropriateness for study participation based on inclusion/exclusion criteria.
- **Brief Physical Examination** – A brief physical exam of the major organ systems will be performed at Visit 1 (screening) to assess the subject’s physical/medical state prior to Visit 2. Adverse events reported during the conduct of the study will be evaluated by organ system with respect to the baseline physical evaluation.
- **Vital Signs** - Collected at Visit 1 (screening) and will include pulse, respiration, heart rate (systolic and diastolic), temperature, height and weight. The height and weight will be used to calculate and confirm the body mass index (BMI) requirement.
- **Urine Pregnancy Assessments** - Urine pregnancy test will be collected (for females of child bearing potential) at Visit 2 prior to treatment. Subjects with a positive result will be excluded from the study.
- **Adverse Event Reporting** – Investigator examination of the treatment area and surrounding anatomy and notation of any observations made by the study investigator of a potential adverse event.
- **Cutometer Elasticity Measurement** – an elasticity measurement use to determine skin pliability prior to, and post treatment. This measurement may serve as an indicator for how the subject’s dermis will behave after exposure to RF treatment (Appendix 6).
- **Numerical Rating Scale (NRS)** – a unidimensional 10-point scale used to measure pain intensity from “no pain” to “worst pain possible” (Appendix 7).
- **Photography** - Standard photo images (2D) and 3D photography using the Vectra XT will be collected for study visits as defined in the protocol. The subject positioning is planned to deliver the following views:
 - “frontal view”;
 - “lateral Right and Left view”;
 - “45⁰ angle Right and Left”.

For reproducibility of the subject’s positioning during the photo session, every effort will be made by the investigator to replicate the same position and facial expressions from

Investigational Device: ThermiRF

Protocol No.: Thermi_0005

Version Date: Final 10-May-2016

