APPENDIX 1 SCHEDE OF EVALUATIONS

	Visit 1 Screening	Visit 2 (Treatment) (n=70)	Visit 3 Day 30	Visit 4 (F/U) Day 60 (n=first 30)	Visit 5 (F/U) Day 90	Visit 6 (F/U) Day 180 (EOS)
Informed consent	X					
Medical /Medication History	X					
Demographics and Baseline Characteristics	X					
Inclusion/Exclusion criteria/conformance	X	X ¹				
Urine Pregnancy Test		X ¹				
Brief Physical Evaluation and Medical Clearance	X					
Vital Signs (incl. Height & Weight)	X					
Photography – 2D (Left, Right and Front views)	X ²			X ²	X ²	X ²
Photography 3D	X ³			X ³	X ³	X ³
Elasticity measurement	X				X	X
Treatment Administration		X				
NRS pain scale			X		X	X
S-GAIS, S-GSQ				X	X	X
P-GAIS, P-GSQ					X	X
Concomitant Medications		X	X		X	X
Adverse events		X	X		X	X

¹ Urine pregnancy test must be conducted prior to treatment

² All 2D images must be collected using standard camera and lighting. Positioning of images must be *Front View, Right and Left Lateral view and Right and Left views at a 45° angle*.

³ All 3D images must be collected using the Vectra XT camera.

⁴ Visit 4 only applies to the first 30 subjects enrolled in the study.

Investigational Device: ThermoRF

Protocol No.: Thermo_0005

Version Date: Final 10-May-2016

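### Section 8.2 accepts a pregnancy test from Visit 1 or Visit 2, while section 9.1 and Appendix 1 place it at Visit 2 before treatment

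*Protocol*

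**What the plan says.** Three places in the Protocol give a visit for the urine pregnancy test.

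- Section 8.2 lists it among the assessments on arrival at Visit 2, with a parenthesis saying that it "must be performed prior to treatment at V1 or V2".
- Section 9.1 says: "Urine pregnancy test will be collected (for females of child bearing potential) at Visit 2 prior to treatment". It adds: "Subjects with a positive result will be excluded from the study".
- Appendix 1 has one mark in the pregnancy-test row, in the Visit 2 column; the Visit 1 cell is blank. The footnote to that mark reads: "Urine pregnancy test must be conducted prior to treatment".

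Section 8 presents the appendix as a picture of its own text: "Study procedures as described in this section are depicted in the schedule of evaluations (Appendix 1").

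On the gap between the two visits, section 8.1 says only: "Enrolled subjects will be scheduled for Visit 2 promptly after Visit 1". The visit list in section 6.1 has "Visit 2: Single Treatment visit", with no day and no window. Section 6.3.2 excludes anyone "Pregnant or planning pregnancy prior to the end of study participation".

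**The concern.** The sections agree that the test comes before treatment. They disagree on whether a test at Visit 1 is enough. A site that works from section 8.2 may rely on a screening result; a site that works from section 9.1 or the schedule tests on the treatment day.

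The difference matters because pregnancy is an exclusion, and Visit 2 involves tumescent infiltration with lidocaine and epinephrine, small incisions and radiofrequency heating. A negative result from an earlier day does not show that the subject is not pregnant on the day of treatment, and the Protocol sets no limit on how much earlier it may be.

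There is also a compliance problem. Section 8.6.1 treats any non-conformance with the Protocol as a deviation, grants no exceptions and tracks them all. A site that uses the Visit 1 option follows section 8.2 and at the same time departs from section 9.1 and Appendix 1.

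**Working it through.** No figure in the plan is at issue and no arithmetic is needed beyond counting. The check sets the sections side by side.

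**1. Which visit is given for the test?**

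| Place | Visit for the test | Accepts a Visit 1 test in place of Visit 2? |
|---|---|---|
| Section 8.2 | Visit 1 or Visit 2, before treatment | Yes |
| Section 9.1 | Visit 2, before treatment | No |
| Appendix 1, pregnancy-test row | Visit 2 column only (1 of 6 columns) | No |

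One of three accepts Visit 1. The Appendix 1 footnote itself names no visit; the column mark does.

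**2. Does the Visit 1 procedure list support the option?** Section 8.1 lists eight assessments: eligibility criteria, history, demographics and baseline characteristics, physical exam, vitals, photography, laxity confirmation and elasticity. Pregnancy tests among them: 0 of 8.

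**3. How old can a Visit 1 result be at treatment?** Of the five visits after screening in section 6.1, Visits 3, 4, 5 and 6 each have a target day and a window. Visit 2 has neither. Section 8.1 asks for prompt scheduling but gives no number of days. Where the investigator prescribes an antibiotic, section 8.1 has the subject start it the day before the procedure, so in those cases at least one day separates the visits. The stated maximum age of an accepted Visit 1 result is therefore: none.

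**4. Does anything else force a fresh test?**

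- Section 8.2 re-verifies eligibility on arrival at Visit 2, but its own parenthesis lets an earlier test meet the pregnancy item.
- In Appendix 1 the Visit 2 eligibility mark carries the same footnote as the pregnancy test. That links the re-check to a test before treatment, but does not say the test must be new.
- The contraception criterion in section 6.3.1 asks sexually active females of childbearing potential to be willing to use birth control. It is not a test.

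**5. Who is affected?** Females of childbearing potential who are tested at Visit 1 and not retested at Visit 2. The documents give no count. The lower limit is 0. The upper limit is the planned enrolment of 70, which is loose because it includes men and, with ages 35 to 65 eligible, is likely to include women past childbearing age.

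**The case against.** The case for leaving this alone, or treating it as purely editorial, runs as follows. The requirement that protects the subject, a test before treatment, is the same in all three places. Section 8.2 lists the test on arrival at Visit 2, so Visit 2 is the default even there, and the parenthesis can be read as a permitted alternative. A stale result needs several steps together: the site adds a Visit 1 test that section 8.1 does not list, omits the one listed for arrival at Visit 2, passes over section 9.1 and the schedule, and lets time go by despite the instruction to schedule promptly. The shared footnote in Appendix 1 ties the Visit 2 eligibility check to the test. The 0 to 70 range says little about real exposure.

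Most of this stands as an argument about weight. The chain of steps makes the event unlikely, and the range is uninformative. It does not remove the conflict. Section 8.2 expressly permits the first two steps, so a site taking them would be following a written instruction. Promptness without a number of days is not a limit that can be monitored. The footnote does not ask for a fresh test. If the alternative was intended, the text is still wrong, because section 9.1 and Appendix 1 do not provide for it.

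One further objection is fair: deleting the Visit 1 option does not by itself write into section 8.2 that the result must be negative or that the test applies to females of childbearing potential. Section 9.1 already limits the test to that group and excludes subjects with a positive result.

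**Conclusion.** The concern holds. Section 8.2 conflicts with section 9.1 and Appendix 1, and nothing else in the Protocol resolves the conflict. As written, section 8.2 allows treatment on a Visit 1 pregnancy result of no stated maximum age.

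The severity is low. It is a consistency correction to a safety check and should be made. No wording lets a female of childbearing potential go untested, and the statistical plan is untouched. The conclusion rests on the wording alone; the one thing not known is how many subjects, if any, would be treated on a Visit 1 result.

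**What to change.** In section 8.2, delete the words V1 or from the parenthesis, so that the test is required at Visit 2 before treatment. Sections 8.1 and 9.1 and Appendix 1 then need no change. If wanted, add a short clause saying that the result must be negative, that the test applies to females of childbearing potential, and that a test at Visit 1 may be added but does not replace the one at Visit 2. This clause is new text in section 8.2, beyond the two-word deletion.

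The cost is a second urine test for any subject already tested at Visit 1. Section 7.3.2 already provides for commercial urine test kits.

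The alternative is to keep the flexibility, by allowing Visit 1 in section 9.1 and Appendix 1 and stating a maximum number of days between the test and treatment. That would also be consistent, but it takes more edits, needs an interval to be chosen and justified, and protects the subject less than a test on the treatment day.

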8.3. Visit 3 (Day 30) - (± 7 to 14 days)

The following assessments will be performed:

- NRS
- AE and ConMed assessment

8.4. VISITS 4 (Days 60) - (± 7 to 14 days)

This visit applies to the first 30 subjects enrolled in the study. During this visit, the following assessments will be performed:

- NRS
- Photography (2D and 3D)
- Questionnaires
 - P-GAIS (Appendix 2)
 - S-GAIS (Appendix 3)
 - P-GSQ (Appendix 4)
 - S-GSQ (Appendix 5)
- AE and ConMed assessment

Investigational Device: ThermiRF

Protocol No.: Thermi_0005

Version Date: Final 10-May-2016

8.5. VISIT 5 and 6 Follow-Up (Days 90 and 180 “EOS”) - (\pm 7 to 14 days)

During these follow-up visits, the following assessments will be performed:

- NRS
- Photography (2D and 3D)
- Elasticity measurement
- Questionnaires
 - S-GAIS
 - P-GAIS
 - SGSQ
 - PGSQ
- AE and ConMed assessment

8.6. Subject Withdrawal and Early Termination

Subjects may withdraw from the study at any time at their own request, or they may be withdrawn at any time at the discretion of the investigator or Sponsor for safety, behavioral, or administrative reasons. Every effort should be made to document subject outcome, if possible. The investigator should inquire about the reason for withdrawal, request the subject return for a final visit, and if applicable, follow-up with the subject regarding any unresolved adverse events.

If the subject withdraws from the study and also withdraws consent for disclosure of future information, no further evaluations will be performed and no additional data will be collected. The Sponsor may retain and continue to use any data collected before such withdrawal of consent.

8.6.1 Protocol Deviations

Protocol deviations will be tracked and managed during the conduct of the study. A protocol deviation is defined as a non-conformance from the protocol which occurs at any time during the conduct of the study. Exceptions will not be granted by the sponsor for any planned or unplanned deviation. All protocol deviations will be tracked.

8.6.2 Status Classification

Classification	Criteria
Screen Failure	Signs the ICD but does not meet entry criteria or withdraws prior to Visit 2.
Enrolled	Signs the ICD and met all inclusion/exclusion criteria
Treated	Signs the ICD and successfully completes V2
Discontinued/Withdrawal	Signed the ICD but does not successfully complete any visits
Completed	Signs the ICD and successfully completes all study visits

9. ASSESSMENTS

9.1. Clinical Evaluations

The following clinical evaluations will be conducted during the study review:

- **Medical and medication history** – An assessment of the participant’s health status prior to enrollment to ascertain appropriateness for study participation based on inclusion/exclusion criteria.
- **Brief Physical Examination** – A brief physical exam of the major organ systems will be performed at Visit 1 (screening) to assess the subject’s physical/medical state prior to Visit 2. Adverse events reported during the conduct of the study will be evaluated by organ system with respect to the baseline physical evaluation.
- **Vital Signs** - Collected at Visit 1 (screening) and will include pulse, respiration, heart rate (systolic and diastolic), temperature, height and weight. The height and weight will be used to calculate and confirm the body mass index (BMI) requirement.
- **Urine Pregnancy Assessments** - Urine pregnancy test will be collected (for females of child bearing potential) at Visit 2 prior to treatment. Subjects with a positive result will be excluded from the study.
- **Adverse Event Reporting** – Investigator examination of the treatment area and surrounding anatomy and notation of any observations made by the study investigator of a potential adverse event.
- **Cutometer Elasticity Measurement** – an elasticity measurement use to determine skin pliability prior to, and post treatment. This measurement may serve as an indicator for how the subject’s dermis will behave after exposure to RF treatment (Appendix 6).
- **Numerical Rating Scale (NRS)** – a unidimensional 10-point scale used to measure pain intensity from “no pain” to “worst pain possible” (Appendix 7).
- **Photography** - Standard photo images (2D) and 3D photography using the Vectra XT will be collected for study visits as defined in the protocol. The subject positioning is planned to deliver the following views:
 - “frontal view”;
 - “lateral Right and Left view”;
 - “45⁰ angle Right and Left”.

For reproducibility of the subject’s positioning during the photo session, every effort will be made by the investigator to replicate the same position and facial expressions from

Investigational Device: ThermiRF

Protocol No.: Thermi_0005

Version Date: Final 10-May-2016

baseline at every required time point. Additionally, every effort will be made by the investigator to ensure the same person (study staff member) will take all photos on the same subject during their participation.

- **Submental Skin Laxity Confirmation:** This assessment integrates three features: skin fat and muscle neck structures and redundancy (horizontal and vertical folds). This assessment will be performed by the investigator to ensure the subject's eligibility at Visit 1.
- **Global Assessment of Improvement Questionnaires:** A subject and physician appraisals of treatment outcomes.

